8.2.1.1 Day 1 (Pre-treatment) Assessments Performed Prior to Each Dose

- Physical examination
- Height and weight
- Vital signs
- Hematology
- Serum chemistry
- Urinalysis
- Pregnancy testing (applicable females only)
- Neurological examination (performed prior to the administration of anesthesia and the HGT-1410 IT injection)
- Concomitant medications, therapies, and procedures
- AE assessments

Note: If the HGT-SAN-055 EOS (or HGT-SAN-067 Screening) assessments were performed within 7 days of first intrathecal HGT-1410 treatment in this study, the pre-treatment assessments described in this section do not need to be completed prior to the first treatment in study HGT-SAN-067.

DAY 1 (PRE-TREATMENT) ADDITIONAL ASSESSMENTS PERFORMED AT MONTHS 12, 24, 36, AND 54

- Head circumference
- Visual and hearing assessments
- Urine heparan sulfate and heparan sulfate derivatives
- Plasma and /or serum heparan sulfate and heparan sulfate derivatives
- Anti-rhHNS antibody testing
- ABR
- MRI of the head
- Full neurodevelopmental testing, including VABS-II (performed prior to the administration of anesthesia and the HGT-1410 IT injection)
- Children's Sleep Habits Rating Scale
- Child health questionnaire-50
- Child health questionnaire-87
- Infant toddler QoL Questionnaire

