10.6 Efficacy, Safety, and Pharmacodynamic Evaluations

10.6.1 Primary Analyses

10.6.1.1 Safety Analysis

In general, safety assessments will be based on all assessments post-baseline. The assessment of safety will be based primarily on the frequency of AEs, and on the frequency of clinically notable abnormal vital sign and laboratory values. Changes from baseline will be calculated by subtracting the baseline value from the post-baseline value.

All enrolled patients who had an IDDD surgical procedure and/or received administration of HGT-1410 will be included in the safety analysis.

Adverse events will be recorded throughout the study and at early termination. Adverse events and medical conditions will be coded using the Medical Dictionary for Regulatory Activities (MedDRA).

Adverse events will be summarized by presenting, for each dose group, the number and percentage of patients having any AE, having an AE in system organ class, and having each individual AE. In addition, those events which resulted in death or were otherwise classified as serious will be presented in a separate listing. The incidence of treatment-emergent adverse events, defined as all AEs from the time of the surgery for IDDD implantation to the last follow up contact, ie, 30 days after the last HGT-1410 administration, (new or worsened from baseline) will be summarized by system organ class, severity, type of adverse event and relationship to trial medication/procedure.

Treatment-emergent AEs deemed related to HGT-1410 administration will be summarized separately.

IDDD, and procedure-related AEs will be summarized within system organ class by preferred term. IDDD and procedure-related AEs will be tabulated by severity (mild, moderate, severe) and degree of relatedness. Separate tabulations will be provided for adverse events related to the IDDD, device surgical procedure (including post-implant infections) and IT administration process. These summaries will be presented by device and overall, as appropriate.

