Descriptive summaries of clinical laboratory evaluations (hematology, serum chemistry, urinalysis and CSF) results will be presented in summary tables by evaluation visit. Changes from baseline will be summarized for each post-baseline visit. Each laboratory result will be categorized as a patient having had (1) an Abnormal and Clinically Significant (CS) value at any time, (2) no CS values at any time but had at least one Abnormal and not CS (NCS) value, and (3) no CS or NCS values at any time; the number and percentage in each category will be presented. For any patient who experiences a CS laboratory result at any time that was not CS at

baseline (or the most recent non-missing value prior to the start of the treatment), their entire profile for that particular laboratory parameter will be presented as a listing.

The observed values and changes from baseline for vital sign data will be summarized for each dose group. Shift tables may be presented, utilizing reference ranges. Patients with notably abnormal values will be identified and listed separately along with their values.

The observed values and changes from baseline for ECG data will be summarized for each dose group. Patients with any clinically significant findings and/or conduction abnormalities will be listed separately along with their values.

Anti-rhHNS antibody formation will be monitored throughout the study. Results will be presented in summary tables by number and percentage of positive and negative specimens by evaluation visit, and number and percentage of positive and negative specimens overall. The effect of antibodies on other safety parameters will be assessed by presenting summary tables by antibody status.

For those patients who fail to complete the study, the reason for discontinuation will be listed by patient and dose group.

Listings of all study safety data will be presented.

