Note: The timing of assessments is calculated from the start of HGT-SAN-055. Therefore, for example, the end-of-study visit, as presented here at Month 54, corresponds to Month 48 in HGT-SAN-067, but represents a total of 54 months of study treatment (48 months in HGT-SAN-067 + 6 months in HGT-SAN-055).

^a Week 1 only, and only performed if >7 days have elapsed since HGT-SAN-055 EOS visit assessments.

^b ECG to be performed following administration of study drug.

^c CSF samples will be obtained according to the process with in the study operations manual). An attempt will be made to obtain a CSF sample via the IDDD prior to each administration of HGT-1410 and at the End of Study visit. If it is not possible to obtain a CSF using the IDDD, the IDDD may be replaced (up to twice in a 6 month period [including the time in the HGT-SAN-055 study]) or a LP may be performed (can occur up to 5 times in a 6 month period).

^d Patients may be discharged as early as 4 hours post HGT-1410 infusion (ie, on Day 2) when deemed clinically stable by the Investigator.

^e Specimens collected once a month, at Day 1 of the first treatment week.

^f All patients who complete the study will have end of study assessments performed 30 (±7 days) after their last dose of study drug.

^g If a patient's IDDD becomes nonfunctional or infected; it will be replaced (up to 2 times in a 6 month period; including the time in Study HGT-SAN-055).

^h The neurological exam should not occur sooner than 4 hours after administration of study drug or before the patient has fully recovered from any anesthesia administered for the dosing, whichever occurs later.

ⁱ Full neurodevelopmental testing includes an assessment with the Vineland Adaptive Behavior Scales, Second Edition (VABS-II)

^j A safety follow up telephone call will be made 30 (±7 days) after End of Study Procedures.

^k Assessments will be required only if more than 60 days have elapsed following the HGT-SAN-055 procedures. These assessments would be repeated within 30 days prior to the first scheduled HGT-1410 IT dose.

Table A1-1 HGT-SAN-067 Study Assessments for Patients Who Have Received 6 Months of HGT-1410 Treatment in Study HGT-SAN-055

Assessment	Screening/or HGT-SAN-055 EOS Visit ^k (Month 6 from the start of HGT-SAN-055)	Dosed every 28 (±7) days (ie, Q4W)		Months 12, 24, 36, and 54 (from the start of HGT-SAN-055)	EOS ^f Month 55 (from the start of HGT-SAN-055)	Month 56 Safety Follow-up ^j

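### The three-class laboratory count ignores baseline and number of tests, so its split between NCS and never abnormal largely tracks length of follow-up and mixes old with new abnormalities

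*Protocol*

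**What the plan says.** Laboratory changes are among the primary safety endpoints (section 3.1). Section 10.6.1.1 plans by-visit summaries and states: "Changes from baseline will be summarized for each post-baseline visit". It then adds a patient-level count: "Each laboratory result will be categorized as a patient having had (1) an Abnormal and Clinically Significant (CS) value at any time"; second, "no CS values at any time but had at least one Abnormal and not CS (NCS) value"; third, "no CS or NCS values at any time; the number and percentage in each category will be presented". A patient with a CS result that was not CS at baseline gets a further output: "their entire profile for that particular laboratory parameter will be presented as a listing". Earlier, the section rests safety primarily on adverse events and "on the frequency of clinically notable abnormal vital sign and laboratory values".

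Hematology, serum chemistry and urinalysis stand under the heading "Day 1 (Pre-treatment) Assessments Performed Prior to Each Dose" (section 8.2.1.1). Dosing is every 28 days (section 6.3), and Appendix 1 counts follow-up as "48 months in HGT-SAN-067 + 6 months in HGT-SAN-055".

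**The concern.** The count has no term for baseline status, number of samples or time at risk. Two things follow.

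- A patient followed longer has more chances of a stray value. The percentage in the NCS class therefore rises with follow-up even if the drug does nothing. Withdrawn patients are not replaced (section 7.27), and there are at most 12 patients in three dose groups, so a few early withdrawals could make groups look different.
- A child with a long-standing mild abnormality falls in the NCS class together with a child who developed one on treatment. The study has no control, so each child's own baseline is the main comparator available, and this table does not use it.

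At stake is whether a reader can see new, mild, non-CS abnormalities, such as a modest rise in a liver enzyme in a few children, at patient level. Visit means can hide a few affected patients, and the listing covers new CS results only.

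**Working it through.** The protocol gives no abnormality rate, so there is no planned figure to reproduce. The inputs are as follows.

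- Samples per parameter, m. Forty-eight months at one per month gives 48. Four years at 28 days gives 4 × 365.25 / 28 = 52.2, so about 52. Footnote a of Appendix 1 describes the Day 1 assessments as Week 1 only. Section 8.2.1.1 requires them before each dose and limits the seven-day exemption to the first, so the monthly reading is used.
- Chance that a result is flagged with no drug effect, p. This is not in the documents. Assumed 2.5% to 5%, two-sided; 5% is what a central 95% reference range gives.
- Within-child correlation of serial results, ρ. This is not in the documents. Assumed 0 to 0.8.

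**Independent results.** P(ever abnormal) = 1 − (1 − p)^m.

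- p = 5%: 1 − 0.95^48 = 1 − 0.0853 = 91.5%; with m = 52, 93.1%.
- p = 2.5%: 1 − 0.975^48 = 1 − 0.2966 = 70.3%; with m = 52, 73.2%.

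**Correlated results.** Use an exchangeable normal model with cut-off c = Φ⁻¹(1 − p/2). Given a child's level u, a result is normal with probability π(u) = Φ((c − √ρ·u)/√(1−ρ)) − Φ((−c − √ρ·u)/√(1−ρ)). Then P(ever abnormal) = 1 − ∫ π(u)^m φ(u) du. By numerical integration:

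| p | ρ | 12 samples | 48 samples | 48 samples, every child shifted by 0.5 SD |
|---|---|---|---|---|
| 5% | 0 | 46% | 91.5% | 98% |
| 5% | 0.5 | 32% | 61% | 68% |
| 5% | 0.7 | 23% | 40% | 47% |
| 5% | 0.8 | 19% | 30% | 36% |
| 2.5% | 0 | 26% | 70% | 88% |
| 2.5% | 0.5 | 18% | 39% | 48% |
| 2.5% | 0.7 | 13% | 24% | 32% |
| 2.5% | 0.8 | 10% | 18% | 24% |

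In every row, going from 12 to 48 samples with no drug effect moves the percentage more than a true half-SD shift in every child does at 48 samples. At p = 5% and ρ = 0.5 the two changes are 29 and 7 points. At p = 2.5% and ρ = 0.8 they are nearly equal, about 7 and 6 points.

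**CS class.** It also accumulates over time, but from a much rarer event that needs a clinical judgement. At assumed rates of 0.1% and 0.5% per result, independent, 1 − 0.999^48 = 4.7% and 1 − 0.995^48 = 21% are ever CS. It stays far from saturation.

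**The case against.** The strongest reply is that the count is one of several laboratory outputs. By-visit changes from baseline precede it and do not inflate with repeated sampling. New CS results are listed in full, and listings of all safety data are promised. Section 7.23.1.1 treats abnormal laboratory values as adverse events, and treatment-emergent events, new or worsened from baseline, are tabulated by severity. All of this stands. It means a laboratory signal has other routes to being seen, although the adverse-event route for a non-CS value depends on the investigator reporting it.

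A reader might infer three stronger things that the documents do not support.

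- That the never-abnormal class empties by chance. This needs a flag rate near 5% and almost independent results. At correlations of 0.7 to 0.8, between 60% and 82% of children stay in it.
- That this is the primary laboratory summary. The protocol does not call it so, and its primary basis, clinically notable values, fits the CS class better than isolated NCS values.
- That the table's form is why a drug effect cannot be isolated. With no control, at most 12 patients and no hypothesis tests, no laboratory table here could do that.

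It can also be said that shift tables belong in the statistical analysis plan, which is not shown. That is fair for detail, but the worst-ever rule itself is fixed in the protocol. Finally, all dose groups share one schedule, so unequal follow-up would arise only through withdrawal or missed tests.

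**Conclusion.** The point holds for the split between NCS and never abnormal. As defined, that split depends heavily on how many times a child was tested, and it does not distinguish pre-existing from new abnormalities. Its chance level at 48 samples lies anywhere from about 18% to 91.5% per parameter under the assumed flag rates and correlations. That width is itself a reason not to read the percentage on its own. The dependence on sample count appears throughout the range examined; how strong it is rests on assumptions the protocol cannot settle. The failure to use baseline rests on no assumption. This is a worthwhile improvement to one table, not a flaw in the safety assessment as a whole.

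**What to change.** In section 10.6.1.1, for each parameter, replace the single worst-ever count with a shift table from baseline category (normal, NCS, CS) to worst post-baseline category, so that new or worsened abnormalities are counted separately from those already present. Present it by 12-month interval, with the number of patients at risk and tests done in each. Keep the CS class and the CS listing as they are.

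CTCAE grades may be added for parameters with a row in CTCAE v3.0. They cannot replace the protocol's own categories throughout: the version reproduced has no row for LDH, BUN, chloride or red-cell indices such as MCV, and it grades white cells only when low. A requirement for two consecutive abnormal values is not needed, and in a safety study this small it would drop isolated results from the summary.

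The cost is a little more table programming.

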3 STUDY ENDPOINTS

3.1 Primary Endpoint

The primary endpoints of this study are related to the long-term safety of intrathecal HGT-1410 administration. The safety endpoints are:

[figure not shown]
- adverse events (type and severity)
- changes in clinical laboratory testing (serum chemistry including liver function tests, hematology, and urinalysis)
- electrocardiograms (ECG)
- cerebrospinal fluid (CSF) chemistries (including cell counts and inflammatory markers)
- anti-rhHNS antibodies (in CSF and serum).

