7.7.5.3 Anti-rhHNS Antibodies

An aliquot of each CSF sample collected will be quick frozen as per the Laboratory and/or Study Operations Manual for subsequent determination of anti-rhHNS antibodies at Shire HGT or Shire HGT designated laboratories.

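### Anti-rhHNS antibodies, a primary endpoint, are summarised only by specimen, so the overall percentage is not the proportion of patients who develop antibodies, and the CSF denominator is not fixed

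*Protocol*

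**What the plan says.** Section 3.1 lists anti-rhHNS antibodies, in both CSF and serum, among the primary safety endpoints. Section 10.6.1.1 then sets their summary: "Results will be presented in summary tables by number and percentage of positive and negative specimens by evaluation visit", and, continuing the same sentence, "number and percentage of positive and negative specimens overall". It gives no number or percentage of patients ever positive or newly positive. Antibody data appear at patient level only as a way of splitting other data: "The effect of antibodies on other safety parameters will be assessed by presenting summary tables by antibody status". The section does not define antibody status. It closes with "Listings of all study safety data will be presented".

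Other repeated outcomes are counted by patient. For adverse events the unit is "the number and percentage of patients having any AE". For laboratory tests, "Each laboratory result will be categorized as a patient having had" one of three categories over all visits. Section 10.6.2.1 reports the proportion of patients with at least one device failure or malfunction.

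On which CSF samples are tested, the protocol says different things:

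- Section 7.7.5.3, on antibodies, says "An aliquot of each CSF sample collected will be quick frozen" for later antibody determination, and Section 6.3.1 has CSF taken before every injection.
- Footnote m of Appendix 1, attached to the CSF collection row, includes antibodies among the CSF tests. That row covers every dosing visit.
- The antibody row of Appendix 1, which names serum and CSF, marks screening, Months 12, 24, 36 and 54, and EOS. Section 8.2.1.1 gives the same four months.
- Section 7.7.5 says which assays each CSF sample receives and cites 7.7.5.1, 7.7.5.2 and 7.7.5.4, leaving out 7.7.5.3.

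**The concern.** The usual immunogenicity question is how many patients develop antibodies. An overall percentage of specimens answers a different one: what share of all samples taken was positive. It mixes how many patients convert with how late they convert, how long they stay positive and how many samples each contributes. With at most 12 patients followed for about four years, these can differ widely.

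The protocol does not leave the unit open. It fixes it, so an analysis plan that follows the text carries it forward. A reader who takes the overall figure as an incidence could be misled in either direction, and the size of the error could not be judged from the table. For CSF, two analysts following different sections would also use very different denominators.

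**Working it through.** The protocol states no antibody rate, so there is no figure of its own to reproduce.

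**Inputs**
- N = 12 patients, the maximum (Section 10.2).
- K, scheduled specimens per patient in one fluid (Appendix 1). For serum, K = 6: screening/Month 6, Months 12, 24, 36, 54 and EOS at Month 55. For CSF on the antibody row, K = 5 for a patient with a Month 54 sample, because CSF is then not repeated at EOS (Section 8.3; Appendix 1, footnote p).
- p, patients ever positive, and m, positive specimens per positive patient. Neither is given. Assumed: p = 6 for illustration, m from 1 to K.

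**Formulas** (one fluid, complete data)
- Patients ever positive = p/N
- Specimens positive overall = (p × m)/(N × K)
- Ratio of the first to the second = K/m, which does not depend on p

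**Results for K = 6, p = 6 (50% of patients)**

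| m | Specimens overall | Understatement |
|---|---|---|
| 1 | 6/72 = 8.3% | 6.0-fold |
| 2 | 12/72 = 16.7% | 3.0-fold |
| 3 | 18/72 = 25.0% | 2.0-fold |
| 4 | 24/72 = 33.3% | 1.5-fold |
| 5 | 30/72 = 41.7% | 1.2-fold |
| 6 | 36/72 = 50.0% | none |

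Positivity from Month 12 onward is m = 5, from Month 24 m = 4, from Month 36 m = 3 and from Month 54 m = 2. A transient response also gives a low m. With K = 5 the ratio runs from 5.0 to 1.0.

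**Unequal follow-up.** Suppose 6 patients are positive on all 6 specimens and 6 negative patients leave after 2. The overall figure is 36/(36 + 12) = 36/48 = 75%, against 50% of patients. If instead the 6 positive patients leave after 2 specimens, both positive, it is 12/(12 + 36) = 25%.

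**By visit.** Each patient has one scheduled specimen per fluid per visit, so within serum or within CSF the specimen percentage equals the percentage of tested patients.

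**CSF denominator.** On the antibody row it is 12 × 5 = 60 for completers. If every pre-dose sample is assayed, 48 months of treatment gives 48 samples per patient at one per calendar month, or 48 × 30.4375/28 = 52.2 at one per 28 days. The denominator is then at least 12 × 48 = 576. How far the percentage moves depends on the time course of positivity, which is unknown. With positivity throughout it does not move.

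**The case against.** The case against is substantial. The by-visit half of the sentence is sound within one fluid. A specimen percentage is correctly labelled and carries information on persistence. Section 10.6.1.1 rests safety mainly on adverse events and on abnormal vital signs and laboratory values. With at most 12 patients and full listings, patient incidence can be counted by hand. Layout by fluid is ordinary detail for an analysis plan, to which Section 10.6.3.2 refers. All of this stands, and it limits the point to the overall summary and the missing patient count. It does not remove the point, because the protocol has chosen a unit for a primary endpoint that differs from the one it uses elsewhere, and readers should not have to rebuild that endpoint from listings.

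Three stronger readings are tempting, and the documents support none of them:

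- A reader might infer that serum and CSF specimens share one denominator, so that negative CSF dilutes positive serum. The protocol never says they are pooled.
- A reader might infer that repeated specimens are treated as independent. For antibodies only counts and percentages are planned, with no interval or test, so no such assumption is made.
- A reader might infer immortal-time bias in the tables by antibody status, with events before seroconversion placed in the positive group. That requires status to mean ever positive, and the protocol does not define it.

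**Conclusion.** The point holds in limited form. The overall specimen percentage is not the proportion of patients who develop antibodies, and the protocol plans no summary that is. Within one fluid with 6 specimens per patient and complete data, the understatement lies between 1.0-fold and 6.0-fold. It reaches 3-fold or more only when positive patients have at most 2 positive specimens. Persistent antibodies from Month 12 give 1.2-fold.

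A general claim of several-fold understatement would go too far: persistence is not known from the documents, and unequal dropout can push the figure above the patient rate. Separately, the sections on CSF antibody testing contradict one another, which leaves the overall CSF summary without a fixed denominator. No data are lost, and the weakness lies in the planned presentation.

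**What to change.** In Section 10.6.1.1 add, separately for serum and CSF, the number and percentage of patients:

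1. positive at each visit, among those tested;
2. ever positive after baseline;
3. newly positive, among those negative at the HGT-SAN-055 baseline.

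Keep the specimen counts as supportive. Reconcile Sections 7.7.5, 7.7.5.3 and 8.2.1.1 with the antibody row and footnote m of Appendix 1, so that they state one CSF antibody testing schedule.

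The statistical part costs protocol wording and table shells, with no extra samples. The number of CSF assays depends on which schedule the sponsor confirms. Section 7.7.5.3 already has an aliquot of each sample frozen, so neither choice needs further collection.
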